6.4. FlexCath Advance Steerable Sheath, 12 Fr

The FlexCath Advance Steerable Sheath, 12 Fr ("sheath") is a percutaneous introducer fitted with a hemostasis valve to allow for introduction, withdrawal and swapping of catheters and wires while minimizing blood loss. A side-port with three-way stopcock is integrated to allow continuous drip infusion, injection through the center lumen, flushing, air or blood aspiration, blood sampling and pressure monitoring. The sheath is intended to allow sheath deflection to facilitate catheter positioning. It is supplied sterile and packaged together with a dilator.

The Indications for Use in Canada and the US: The FlexCath Advance Steerable Sheath is intended for percutaneous catheter introduction into the vasculature and into the chambers of the heart. The sheath deflection facilitates catheter positioning.

Investigational Note: As the sheath Instructions For Use for both Canada and the US states it can accommodate devices up to 10.5Fr, and the ArcticLine Catheter is 11Fr, the sheath will be used investigationaly for the purposes of the study.

6.5. Arctic Front Advance Cryoablation Catheter and Related Devices

The Arctic Front Advance ("AFA") Cardiac Cryoablation Catheter is a sterile, single use, minimally invasive intravascular balloon catheter specifically designed for tissue cryoablation. The AFA Catheter is used together with the CryoConsole and related devices. The AFA Catheter is percutaneously advanced to the heart chamber from the femoral access via a transseptal sheath in

the vasculature. Once the catheter reaches the left atrium, the balloon is inflated and the cooling segment creates circumferential lesions at the antrum of the targeted pulmonary veins.

Licensed indication in Canada: The Arctic Front Advance Cardiac Cryoablation Catheter is indicated for the treatment of patients with atrial fibrillation.

Approved indication in US: The Arctic Front Advance Cardiac Cryoablation Catheters are indicated for the treatment of drug refractory recurrent symptomatic paroxysmal atrial fibrillation.

Investigational Note: As the US Arctic Front Advance IFU does not include treatment of persistent atrial fibrillation, any use of the device at a US study center will be considered investigational.

The Achieve and Achieve Advance Mapping Catheter (“Achieve/Achieve Advance mapping catheter”) and the Manual Retraction Kit are used in conjunction with the Arctic Front Advance catheter as described below.

The Achieve/Achieve Advance mapping catheter is an intra-cardiac electrophysiology diagnostic catheter indicated for multiple electrode electrophysiological mapping of the cardiac structures of the heart, i.e., recording or stimulation only. The Achieve/Achieve Advance mapping catheter is designed to obtain electrograms in the atrial regions of the heart.

The Indications for Use in Canada and the US: The Achieve/Achieve Advance mapping catheter is indicated for multiple electrode electrophysiological mapping of the cardiac structures of the heart, i.e. recording or stimulation only. The Achieve/Achieve Advance mapping catheter is designed to obtain electrograms in the atrial regions of the heart.

The Manual Retraction Kit contains one large syringe, one 3-way stopcock and a coaxial-to-Luer adaptor. The kit is used during the rewrap procedure of the Arctic Front Advance catheter if the Investigator cannot retract the catheter using the normal catheter retraction cycle.

6.6. Freezor MAX Cryoablation Catheter

The Freezor MAX Cardiac Cryoablation Catheter (“Freezor MAX”) is a sterile, single use, flexible, steerable catheter used to ablate cardiac tissue. It is used together with the CryoConsole and related devices. The 8mm tip of the focal Freezor MAX reaches cryoablation temperatures when refrigerant is injected from the CryoConsole to the tip of the catheter. The catheter tip has an integrated thermocouple for temperature reading capability. The catheter is introduced into the vasculature by traditional minimally invasive techniques.

Licensed indication in Canada: The Freezor MAX Cardiac Cryoablation Catheter is intended for use in treatment of cardiac arrhythmias.

Approved indication in US: The Freezor MAX Cardiac Cryoablation Catheters is indicated for use as an adjunctive device in the endocardial treatment of paroxysmal atrial fibrillation in conjunction with the Arctic Front Advance Cardiac Cryoablation Catheter for the following uses: gap cryoablation to complete electrical isolation of the pulmonary veins, cryoablation of focal trigger sites and creation of ablation line between the inferior vena cava and the tricuspid valve.

Investigational Note: As the US Freezor MAX IFU does not include treatment of persistent atrial fibrillation, any use of the device at a US study center will be considered investigational.

6.7. Packaging

In Canada and the US, the ArcticLine Catheter will be labeled as investigational. The sheath will not be labeled as investigational, as this device will be considered investigational upon opening and introduction into the vasculature per the CIP. The Achieve/Achieve Advance mapping catheter will not be labeled as investigational, as these devices will be used on label in the Study.

In Canada, the AFA and Freezor MAX catheters will not be labeled as investigational, as these devices will be used on label in the Study.

In the US, the AFA and Freezor MAX catheters will not be labeled as investigational, as these devices will be considered investigational upon opening and introduction into the vasculature per the CIP.

6.8. Product Training Requirements

Only the Principal Investigator at each study center will be permitted to perform the ArcticLine Catheter ablation procedure. In addition to the Principal Investigator, sub-investigators who have adequate experience with AFA [i.e. 20 independent cases], as deemed by Medtronic, will be permitted to perform the PVI portion of the procedure but will not be allowed to handle the ArcticLine catheter. Investigators responsible as primary operators for the ArcticLine Catheter ablation procedure will be required to undergo product training (to include hands on experience in an In Vitro, In Vivo [animal], and human cadaver model) prior to the site's first subject enrollment. A separate training document will overview topics and include details on the format of delivery.

6.9. Product Receipt, Tracking and Return

The study will utilize the commercially available sheath, AFA and Freezor MAX with no study driven changes to the product or labeling. These devices will not be provided to the centers. Product tracking considerations by device type:

- Sheath: Considered investigational in both Canada and the US when opened and introduced into the vasculature.
- AFA: Considered investigational in the US when opened and introduced into the vasculature; non-investigational in Canada.
- Freezor MAX: Considered investigational in the US when opened and introduced into the vasculature; non-investigational in Canada.

The ArcticLine Catheter Files will be stored on flash drives and uploaded by Medtronic personnel (e.g. Field Clinical Engineers) to the CryoConsoles identified at each study site. The flash drives will not be handled directly by study site personnel and will remain in the possession of Medtronic personnel for the duration of study enrollment. Once a Catheter File is installed on a site's CryoConsole, Medtronic personnel will affix a label denoting the presence of investigational software. See Appendix A for the example text of the CryoConsole investigational label. Once study enrollment is completed, the ArcticLine Catheter File will be uninstalled from the CryoConsole by Medtronic personnel. Medtronic will manage the device accountability for the Catheter File and provide each site with a copy of the device disposition log.

The following products are to be returned to Medtronic by each study site:

- All ArcticLine Catheters, including expired catheters or those remaining after conclusion of the study
- Any AFA or Freezor MAX catheter with a reportable device deficiency
- Any sheath used in conjunction with an ArcticLine Catheter with a reportable device deficiency

Device disposition logs will be provided to all centers and used for tracking of all investigational product throughout the duration of the study, except for the Catheter File device disposition log which will be owned by Medtronic as noted above. The logs must be maintained and updated when product is disposed of or returned to Medtronic.

6.10. Product Storage

ArcticLine Catheters are investigational and will be maintained in locked, secure storage with access limited only to approved study staff.

7. Selection of Subjects

7.1. Study Population

The study population being studied are patients with documented persistent atrial fibrillation, or those with persistent atrial fibrillation and a history of, or inducible, typical atrial flutter, and generally good cardiovascular health.

7.2. Subject Enrollment

Patients will be screened to ensure they meet all inclusion criteria and none of the exclusion criteria prior to study enrollment, as appropriate. IRB/REB/MEC and Medtronic approval of this CIP and the patient Informed Consent Form must be obtained prior to enrolling subjects in the study.

Enrollment of the subject must occur prior to performing any study procedures. Subjects are enrolled at the time the patient Informed Consent Form is signed and dated. The study will allow for up to 15 subjects to be enrolled and treated with the ArcticLine Catheter.

7.3. Inclusion Criteria

- Documentation of symptomatic persistent AF:
 - Defined as having a continuous episode that is sustained beyond 7 days documented via consecutive ECG recordings, or
 - Defined as having a continuous episode that is sustained beyond 7 days documented by an ECG recording and one doctor note indicating the patient had symptoms consistent with AF
- Age 18 through 80 years old
- Failure or intolerance of at least one Class I or III antiarrhythmic drug
- Subject is able and willing to consent to participate in the study and will commit to completion of all follow-up requirements

7.4. Exclusion Criteria

- Longstanding persistent AF, defined as continuous AF greater than 12 month duration
- Left atrial diameter greater than 5.0 cm
- Active systemic infection
- History of thromboembolic event within the past 6 months or evidence of intracardiac thrombus at the time of the procedure
- Prior left atrial ablation attempt, with exception of:
 - Any pulmonary vein isolation attempt to treat AF, or
 - Successful ablation to treat Wolff-Parkinson White syndrome
- History of left atrial tachycardia
- History of cardiac ablation within 90 days of planned clinical study procedure

- Planned concomitant ventricular ablation¹⁶
- Cryoglobulinemia
- Structural heart disease of clinical significance including:
 - NYHA Class IV Heart Failure
 - Diagnosed with NYHA Class III Heart Failure for more than six months at time of the study ablation procedure
 - LVEF less than 35%
 - Any cardiac surgery (e.g. CABG) within 3 months of the ablation procedure
 - Any mechanical heart valve, prior aortic or tricuspid valve replacement (e.g. valvotomy, valve replacement), or tricuspid valve repair
 - Severe mitral valve regurgitation or stenosis
 - Significant congenital anomaly or anatomy unable to accommodate device
- Prior surgical maze procedure
- Unstable angina
- Myocardial infarction within 3 months of the ablation procedure
- Presence of primum or secundum atrial septal defect
- Anomalous pulmonary venous return
- Prior surgery for congenital heart disease, including atrial septal defect
- Hypertrophic cardiomyopathy with LV septal wall thickness >1.5 cm
- Uncontrolled hyperthyroidism
- Thrombocytosis, thrombocytopenia (including history of heparin-induced thrombocytopenia)
- Severe comorbidity or poor general physical/mental health that, in the opinion of the investigator, will not allow the subject to be a good study candidate
- History of blood clotting or bleeding abnormalities
- Contraindication to all anticoagulation (e.g. novel oral anticoagulants, heparin or warfarin)
- Pregnant, nursing or planning to become pregnant during study duration
- Enrollment in another clinical trial without prior approval from Medtronic
- Presence or use of left atrial appendage closure device
- Presence of or planned implantation of a pacemaker, implantable cardiac defibrillator, implantable loop recorder or cardiac resynchronization device with permanent lead placement
- Pre-existing hemidiaphragmatic paralysis
- Life expectancy less than one year
- Known drug or alcohol dependency
- Existing pulmonary vein stent(s)

¹⁶ Concomitant ventricular ablation will be allowed in the proposed feasibility clinical study if determined to be in the best interest of the subject at the time of the procedure as assessed by the Investigator. However, the ArcticLine Catheter may not be used for these purposes.

Note: For exclusion criteria that cannot be fully assessed in a subject at the time of baseline, but are found to be met during the procedure (e.g. left atrial tachycardia, anatomy unable to accommodate the device), the subject will be exited from the study at that time.

8. Study Procedures

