8.4.5. Pulmonary Vein Cryablation with Arctic Front Advance Catheter

Subjects will be evaluated to determine the need for PVI. If the need is confirmed based on intracardiac electrogram recordings, every effort consistent with subject welfare should be made to treat all PVs or their anomalous equivalents where electrical activity is noted.

Subjects in the Study who require pulmonary vein isolation are to be treated as follows:

- As stated in Section 8.4, perform a baseline voltage map of the left atrium using a 3D mapping system.
- Phrenic nerve monitoring must be done in accordance with Table 4.
- Ablate the pulmonary veins using the Arctic Front Advance Catheter according to the IFU.
- Each pulmonary vein must be assessed for entrance block to demonstrate electrical isolation. Optionally, pulmonary vein assessment for exit block may be performed.
- Perform repeat voltage mapping of the left atrium using a 3D mapping system.

Notes:

- Upon the Investigator's assessment of procedure completion, Isoproterenol and/or adenosine may be used to further assess pulmonary vein isolation.
- Freezor MAX should be used for any gap completion or other FDA approved ablation catheter. In the event another catheter is used instead of Freezor MAX for gap completion, the subject will be exited from the study.

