8.4.6. Linear Cryoablation with ArcticLine Catheter: Roof and Posterior Wall

Once confirmation all pulmonary veins have been isolated and the investigator determines the subject should move forward with ArcticLine ablation, perform the following steps:

Withdraw and remove the Arctic Front Advance catheter through the FlexCath Advance sheath.

Phrenic nerve monitoring must be done in accordance with Table 4. Insert and advance ArcticLine Catheter into the left atrium via the FlexCath Advance sheath and position as follows:

- Roof: Position the ArcticLine Catheter between the right and left superior pulmonary veins.
- Posterior wall: Position ArcticLine Catheter between the inferior pulmonary veins.

Repeat the following steps for both the roof and posterior wall locations:

- Assess the positioning and contact via fluoroscopy, ultrasound imaging, or other visualization technique. Reposition as needed.
- Perform the cryoablation. Cryoapplications of three (3) minutes is recommended for the roof and posterior wall targets in the left atrium.
- At the investigator's discretion, use pacing maneuvers to determine the immediate effect of the ArcticLine ablation(s).
- Note: It is the investigator's discretion to assess necessity of additional freezes to complete the desired ablation line.

Once the roof line and posterior wall lines are completed, assess the posterior wall for isolation using pacing maneuvers and/or 3D mapping.

If no further ArcticLine ablation(s) in the left atrium will be performed:

- Repeat voltage mapping of the left atrium using a 3D mapping system after a minimum 30-minute wait time from the last ArcticLine ablation for each respective anatomy target.
- Use of 3-D mapping following the 30-minute waiting period should be performed while the subject is in Sinus Rhythm.

Notes:

- The ArcticLine Catheter ablation segment should be completely outside of the sheath prior to initiating the ablation. Freezing in the sheath may result in occluding the saline drip.
- Upon the Investigator's assessment of procedure completion, Isoproterenol and/or adenosine may be used to further assess pulmonary vein conduction.
- Use of another catheter, other than the ArcticLine Catheter, for gap completion of the roof and/or posterior wall lines will be considered a treatment failure.

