8.12. Subject Withdrawal or Discontinuation

A subject can withdraw from the study at any time. If the subject wishes to exit early from the study, the center is required to document the reason for exit on an eCRF and in the subject's medical record. In addition, centers shall follow the regulations set forth by their IRB/REB/MEC.

It is recommended that Investigators follow the subject until all device and/or procedure-related adverse events are recovered / resolved or unresolved with no further actions planned. Following completion of the 6 month visit (or after the 6 month visit due CIP v4 follow-up requirements) or early study exit, subjects will continue to receive standard medical care. All data available through the time of the subject's exit will be used for analysis.

Reasons for early study exit include:

- Subject lost to follow-up
- Subject did not meet inclusion/exclusion criteria after consent and did not undergo an ablation procedure
- ArcticLine Catheter was not used during the subject's ablation procedure
- Subject did not provide consent or data use protection authorization
- Subject chooses to withdraw (e.g., consent withdrawal, relocation to another geographic location)
- Investigator deems withdrawal necessary (e.g., medically justified, inclusion/exclusion criteria not met, failure of subject to maintain adequate study compliance)
- The sponsor decides the study will be closed or a particular center will be closed.

In the case that the subject is determined to be lost to follow-up, details of a minimum of two attempts and the method of attempt (e.g., one letter and one phone record or two letters) to contact the subject must be recorded.

An unscheduled office visit should be attempted if the subject exits the study outside of a scheduled follow-up visit. Subjects treated with the ArcticLine Catheter who exit from the study should continue to be followed by an electrophysiologist for follow-up of any potential adverse events at the recommended interval of 6 months from the index ArcticLine Catheter ablation procedure.

For subjects who have not undergone treatment with the ArcticLine Catheter, a new subject may be enrolled to achieve the target sample size of N=15 treated subjects in the Study.

9. Risks and Benefits

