10.3. Reporting of Adverse Events, including Death

For the purposes of the study, all Adverse Events will be collected starting at the time of signing the IC Form through the duration of the subject's participation in the study.

Reporting of these events to Medtronic will occur on an AE eCRF, including a description of AE, date of onset of AE, date of awareness of center, treatment, resolution, assessment of both the seriousness and the relatedness to the investigational device. Each AE must be recorded on a separate AE eCRF. Exceptions include:

- Documented pre-existing conditions are not considered AEs unless the nature or severity of the condition has worsened. Additionally, arrhythmia episodes that are not new or worsening conditions and for which no action is taken are not reportable as AEs.
- Unavoidable Adverse Events, listed in Table 6: Adverse Event and Device Deficiency Definitions need not be reported unless the adverse event worsens or is present outside the stated timeframe after the ablation procedure.
- Cardioversions (DC or Drug) for recurrent symptomatic atrial fibrillation and other atrial arrhythmias are not considered serious adverse events.

Where the definition indicates "device", it refers to any device used in the study. This might be the catheter, or any other component of the system under investigation, or any market-released component of the system.

For any changes in status of a previously reported adverse event (i.e. change in actions taken, change in outcome, change in relatedness), an update to the original AE must be provided. All adverse events must be followed until the adverse event has been resolved, the subject exits the study or until study closure, whichever occurs first.

At the time of study exit, all collected AEs with an outcome of "not recovered/not resolved", "recovering/resolving" or "unknown" must be reviewed and updates provided as applicable.

All reported adverse events will be reviewed by a Medtronic representative. AEs will be classified according to the definitions provided.

Upon receipt of adverse events at Medtronic, a Medtronic representative will review the adverse event for completeness and accuracy and when necessary will request clarification and/or additional information from the Investigator. Medtronic will utilize MedDRA, the Medical Dictionary for Regulatory Activities, to assign a MedDRA term for each adverse event based on the information provided by the Investigator.

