12.1. Primary Objective

Estimate the incidence of ArcticLine Catheter-related and ArcticLine cryoablation procedure-related serious adverse events (SAEs) with an onset date within 7 days post-procedure.

Endpoint Definition

ArcticLine Catheter-related or ArcticLine cryoablation procedure-related SAEs, with an onset date within 7 days post-procedure (except as noted below), as adjudicated by the Clinical Events Committee (CEC), described as follows:

- Atrioesophageal fistula*
 - * Includes atrioesophageal fistula with an onset date at any time after the study cryoablation procedure and is adjudicated by the CEC as either ArcticLine Catheter-related or ArcticLine cryoablation procedure-related.
- Cardiac perforation/tamponade
- Cerebrovascular accident
- Death
- Esophageal injury
- Major bleeding
- Myocardial infarction
- Pericarditis
- Phrenic nerve injury (ongoing at hospital discharge)
- Transient ischemic attack
- Vagal nerve injury resulting in esophageal dysmotility or gastroparesis
- Vascular access complications

Sample Size

The sample size of 15 treated subjects for this study was chosen with the goal to collect preliminary safety and effectiveness data on the ArcticLine Catheter's use in both the left and right atrium.

Analysis Methods

The percentage of catheter related and cryoablation procedure related SAEs will be calculated as the number of procedures with at least one SAE meeting the endpoint definition divided by the number of cryoablation procedures. Each procedure will count, so subjects with repeat cryoablations will contribute more than once to the denominator. Exact methods will be used to construct a 95% confidence interval for the percentage of procedures with an SAE.

Determination of Patients for Analysis

All ArcticLine cryoablation procedures will be included. An ArcticLine cryoablation procedure is considered to have occurred once the ArcticLine Catheter is introduced into the vasculature.

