7.4 Handling of Missing, Unused, and Spurious Data and Dropouts

Subjects who (A) exit the study prior to completion of a phone conversation or follow-up visit 7 or more days after the index procedure and (B) do not have a primary safety event on or before discharge from the index ablation will be considered as missing for the primary endpoint analysis, on grounds that the assessment of the endpoint is incomplete. Subjects with early exits occurring after the one-week phone call will still be included, however: after 7 days post-index ablation, only the atrioesophageal fistula component, which occurs in less than one in 10,000 cryoballoon ablations¹, counts toward the primary endpoint. Therefore, the likely impact of failing to observe new occurrences of the primary endpoint in subjects not followed past one week is negligible. No effort to statistically impute missing data will be made for the primary endpoint or any ancillary endpoints; all such analyses will be "complete cases" and assume that observed missingness occurs completely at random with respect to the outcome.

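### The intra-procedural exit rules are not limited to the time before ArcticLine is introduced, so an exposed subject can leave mandatory safety collection and drop out of the 15-subject primary endpoint

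*Protocol*

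**What the plan says.** **Exit rules.** The Note closing protocol section 7.4 deals with exclusion criteria that could not be fully assessed at baseline. When one is "found to be met during the procedure (e.g. left atrial tachycardia, anatomy unable to accommodate the device), the subject will be exited from the study", exit is immediate, and the Note does not say whether ArcticLine may already have been introduced. A second rule stands in the notes to section 8.4.5, on pulmonary vein gaps: "In the event another catheter is used instead of Freezor MAX for gap completion, the subject will be exited from the study". It has no time limit either. Section 8.4.6 allows vein conduction to be tested again once the lines are made: "Isoproterenol and/or adenosine may be used to further assess pulmonary vein conduction".

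**Exposure.** Section 12.1 fixes the start of exposure: "An ArcticLine cryoablation procedure is considered to have occurred once the ArcticLine Catheter is introduced into the vasculature". All such procedures belong to the primary objective.

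**After exit.** Section 10.3 states that "all Adverse Events will be collected starting at the time of signing the IC Form through the duration of the subject's participation in the study". Section 8.12 adds: "All data available through the time of the subject's exit will be used for analysis". Sections 8.8.4 and 8.12 say that an unscheduled visit should occur or be attempted at early exit. Section 8.12 also recommends following device- or procedure-related events until they resolve or need no further action, and advises that treated subjects who exit be followed by an electrophysiologist. Section 5.1 does not replace treated subjects.

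**SAP.** Under section 7.4, a subject who exits before a contact at 7 or more days and has no primary event by discharge "will be considered as missing for the primary endpoint analysis". That section assumes missingness completely at random. Separately, SAP sections 7.1.2 and 7.1.3 leave out subjects who do not meet the entry criteria at the procedure.

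**The concern.** The population for the primary objective is defined by exposure, but the exit rules are defined by eligibility and by technique. The two can collide in one subject. If the catheter has been introduced and the anatomy then proves unsuitable, section 12.1 counts the procedure while the Note removes the subject from the study.

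What is lost is the safety window: the rest of the first 7 days, late atrioesophageal fistula (which the primary endpoint counts at any time), and the 6-month events of ancillary objectives 5 and 7. The loss would not be random. These exits arise because the procedure was difficult, and difficulty may well be related to device or procedural harm. In a first-in-human study of 15 treated subjects, each one is 1/15 = 6.7% of the denominator.

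**Working it through.** **1. Can exit follow exposure?**

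- *Section 7.4 Note.* Yes. Its anatomy example can become apparent after introduction, and the Note has no cut-off.
- *Section 8.4.5.* Possible but less likely. Section 8.4.6 starts only after all veins are isolated. A later exit needs an optional drug re-test, a reconnection, and the choice of a catheter other than Freezor MAX.
- *Section 8.4.1* (the investigator decides not to go on to ArcticLine) and the section 8.12 reason that ArcticLine was not used. No; both lie before exposure.

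**2. Do the passages agree?** They do not.

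- In section 8.4.5, one sentence allows another approved catheter for gap completion, and the next exits the subject for its use.
- Section 8.7 runs repeat ablation by the section 8.4 procedure and classes radiofrequency touch-up of a vein as treatment failure, where section 8.4.5 says exit.
- Sections 8.4.1 and 8.4.6 to 8.4.8 class the use of another catheter on a line as treatment failure, with no exit.

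**3. The plan's own figure.** SAP section 6 gives a width of 32% for the exact 95% interval with 1 event in 15 procedures. The Clopper-Pearson limits are:

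- lower = Beta quantile(0.025; x, n − x + 1)
- upper = Beta quantile(0.975; x + 1, n − x)

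With x = 1 and n = 15 this gives 0.17% to 31.95%, width 31.8%, which reproduces the 32%.

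**4. Effect of a lost subject.** The number exited and the event status are assumptions; the documents give neither. When x = 0 the upper limit is 1 − 0.025^(1/n), so for n = 14 it is 1 − 0.025^(1/14) = 23.2%.

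| Assumed situation | Subject kept | Subject dropped |
|---|---|---|
| One exited subject, with a day-3 event after discharge; no other events | 1/15 = 6.7% (0.2 to 31.9%) | 0/14 = 0% (0 to 23.2%) |
| Two exited subjects, both with such events; no other events | 2/15 = 13.3% (1.7 to 40.5%) | 0/13 = 0% (0 to 24.7%) |
| One exited subject without an event; one event in another subject | 1/15 = 6.7%, width 31.8% | 1/14 = 7.1%, width 33.7% |

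The first two rows lower the estimate; the third raises it and widens the interval.

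**5. Which rule causes the drop?** For exits under the Note, SAP sections 7.1.2 and 7.1.3 would remove the subject even with complete follow-up. Missing follow-up and the analysis-set restriction therefore each produce 0/14, and correcting only one changes nothing. For exits under section 8.4.5 the subject may be fully eligible, and the SAP 7.4 missing-data rule alone causes the drop.

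**The case against.** Several points against the concern carry weight.

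- *Tachycardia.* A reader might infer that a left atrial tachycardia first provoked by the ArcticLine lesions forces exit. The documents do not support this. The criterion in section 7.4 is a history of left atrial tachycardia, and the Note applies to listed criteria found late. Its shorthand omits the word history, which is a wording fault only.
- *No follow-up at all.* A reader might infer that events after exit can never be known. Section 8.8.4 says an unscheduled visit should take place at early exit and makes adverse event assessment part of it. Section 8.12 recommends clinical follow-up. Retention is weakened, not abolished. Still, none of this keeps the 1-week contact, mandatory reporting or committee adjudication in place.
- *Bias towards the device.* A reader might infer that every such loss flatters the catheter. It does not: losing an event-free subject raises the rate, and the SAP 7.4 missing-data rule spares a subject with a primary event by discharge. For chronic success, subjects without confirmed acute block are left out in any case.
- *Timing.* SAP version 3 (section 7.2.2) says that all procedures are complete, with no repeat ablations done or to come. Rewording cannot change those procedures, and the section 8.7 conflict has no further effect here. Section 7.7 gives a final cohort of 15. With the cap of 15 treated and no replacement, this suggests that no exposed subject was dropped, but does not prove it: the ArcticLine Treated set is itself drawn from subjects eligible at the procedure.

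The Note's missing cut-off stands, as does its conflict with the exposure-based definition in section 12.1.

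**Conclusion.** The concern holds for the Note to protocol section 7.4 and, with lower likelihood, for section 8.4.5. Followed as written, these rules can take an exposed subject out of mandatory safety collection and out of the primary denominator for reasons tied to procedural difficulty. That makes the completely-at-random assumption in SAP section 7.4 doubtful. The direction of bias is not fixed, but a post-discharge event in such a subject would not be counted.

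The size, one subject moving 1/15 (6.7%) to 0/14 (0%) and the upper limit from 31.9% to 23.2%, is an illustration. It assumes one exposed, exited subject with a day-3 event after discharge and no other events. For exits under the Note, the SAP eligibility restriction produces the same drop, so the effect cannot be credited to the exit rule alone. The documents do not say whether any exposed subject was exited, and nothing here shows that one was. This should be fixed; with procedures complete and no frequency known, it does not rank as critical.

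**What to change.** 1. State in the section 7.4 Note and in section 8.4.5 that study exit applies only before ArcticLine has been introduced into the vasculature. After introduction, record the finding as a deviation or treatment failure, and keep the subject in the scheduled safety follow-up through 6 months and in the primary denominator.
2. Amend SAP sections 7.1.2 and 7.1.3 at the same time, so that an exposed subject found ineligible stays in the primary and safety analyses, as protocol section 12.1 requires.
3. Word the Note's tachycardia example as a history of left atrial tachycardia, to match the criterion. Reconcile the two sentences of section 8.4.5 with each other and with section 8.7.
4. Since procedures are complete, check the disposition records for any subject in whom the catheter was introduced and who was then exited. Obtain that subject's 7-day and 6-month adverse event status and report it in the primary and safety analyses. If there is none, say so in the final report.
5. Carry the corrected wording into the future pivotal study.

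*Cost.* A few sentences in the protocol and SAP, with the approvals of section 14.5 if the protocol is formally amended, plus a disposition check and, at most, status retrieval for a few subjects. No extra patients and no new visits are needed, because the 1-week, 3-month and 6-month contacts are already scheduled.
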